8.1.6 Electrocardiogram

The 12-lead ECG will be recorded with a validated ECG device. The parameters for heart rate (HR), PR interval, RR, QRS, QT and QTc(F) will be assessed (i.e., QT correction according to the Fridericia formula $QTcF=QT/RR^{0.33}$). ECG recordings will capture at least

four QRS complexes, i.e., evaluable RR intervals. The Investigator or designee will evaluate whether the ECG is normal or abnormal and whether it is clinically significant, if abnormal. Any occurrence or de- or re-polarization disorders, arrhythmic disorders or other abnormalities will be assessed and any changes compared to the baseline (i.e., predose, treatment day 0) record will be commented. Clinically significant abnormal findings will be reported as AEs.

Additional ECGs may be collected by the Investigator for safety reasons.

8.1.7 Pharmacodynamics

Samples for the determination of IgG and F(ab')₂ fragment levels (total and ADAMTS13 specific) in serum (PD) will be taken at the times presented in the study flow chart. The date and actual time of collection of each sample will be recorded on the laboratory requisition form and in the CRF. Samples will be analysed with electroluminescence based immunoassays using the MSD (Meso Scale Diagnostic) technology. The analyses will be performed at [REDACTED]. Full details of the analytical method used and the analysis results will be detailed in a separate bioanalytical report.

8.1.8 Pharmacokinetics

Samples for determination of concentrations of IdeS in serum will be taken at the times presented in the study flow chart. The actual date and time of collection of each sample will be recorded on the laboratory requisition form and in the CRF. Samples will be analysed by an electroluminescence based immunoassay using the MSD technology. The analyses will be performed at [REDACTED]. Full details of the analytical method used and the analysis results will be detailed in a separate bioanalytical report.

8.1.9 Immunogenicity

Samples for the determination of anti-drug antibody (ADA) levels in serum will be taken at the times presented in the study flow chart. The date and time of collection of each sample will be recorded on the laboratory requisition form and in the CRF. Samples will be analysed for anti-IdeS IgG using a customized IdeS ImmunoCAP test, developed by [REDACTED]. The analysis will be performed by [REDACTED]. Full details of the analytical method used and the analysis results will be detailed in a separate bioanalytical report.

8.1.10 [REDACTED]

8.2 Other Assessments

8.2.1 ImmunoCAP anti-IdeS IgE

A sample for detection of anti-IdeS antibodies of IgE type will be taken at screening. The sample will be sent for analysis at [REDACTED]. Full details of the analytical method used and the analysis results will be detailed in a separate bioanalytical report.

8.2.2 Demographics and Baseline Data

Information about gender, race, date of birth, body weight and height will be collected at the screening visit for each subject. Weight will also be recorded predose on the day of dosing as well as on day 14, 30 and 64. Measurements should be taken without shoes. Body mass index will be calculated from the height and weight. Medical history will be recorded at screening and at day 0.

8.2.3 Physical Examinations

A complete physical examination will be performed at screening, day 30 and on day 64 and include an assessment of the following: general appearance, head and neck (including ears, eyes, nose, mouth and throat), lymph nodes, abdomen, musculo-skeletal, cardiovascular, respiratory, gross neurological examination, skin and urinary system.

8.2.4 Body Temperature

Body temperature will be measured at screening and study visit 2. At visit 2/dosing, body temperature will be recorded pre-dose, 2, 6 and 24 hours post-dose as well as on days 14, 30 and 64.

8.2.5 Serology

Determination of HIV-1 and HIV-2 antibodies, hepatitis B surface-antigen and hepatitis C virus antibodies will be performed at screening for eligibility purposes.

8.2.6 Pregnancy Test

Serum β -hCG will be determined at screening, per-dose and at the end of study (EOS) visit, using validated standard methods.

8.2.7 Prior and Concomitant Medication

Information about prior and concomitant medication will be collected for each patient throughout the study.

8.2.8 Handling of Biological Samples

A detailed description of all sample collections and shipment procedures will be included in a separate laboratory manual. The sponsor or third part(ies) will store the blood samples for up to 2 years after reporting the trial.

8.3 Concomitant Medication

Therapeutic IgG based drugs such as Rituximab will be cleaved by IdeS during 7 days following dosing therefore Rituximab treatment within 7 days prior to IdeS dosing is not allowed (See Section 6.1.2). Other concomitant medication may be administered at the discretion of the Investigator. All concomitant medication, including premedication and prophylactic antibiotics will be recorded in the CRF, together with the main reason for its prescription.

8.3.1 Premedication

Patients will receive premedication with Solu-Medrol 250 mg i.v. and 10 mg loratadine p.o. before the IdeS infusion.

8.3.2 Prophylactic Antibiotic

All patients will receive a two-week regimen of Penicillin V (or alternatively Ciprofloxacin in case of allergy to penicillin) from the start of IdeS treatment.

8.4 Safety

It is of the utmost importance that all staff involved in the study is familiar with the content of this section. The principal investigator is responsible for ensuring this.

8.4.1 Definition of Adverse Events

An adverse event (AE) is the development of an undesirable medical condition or the deterioration of a pre-existing medical condition following or during exposure to a pharmaceutical product, whether or not considered causally related to the product. Relationship to the study drug will be deemed as not related, unlikely, possible or probable. An undesirable medical condition can be symptoms (e.g., nausea and chest pain), signs (e.g., tachycardia and enlarged liver) or the abnormal results of an investigation (e.g., laboratory findings and electrocardiograms).

In cases of surgical or diagnostic procedures, the condition/illness leading to such a procedure is considered as the AE rather than the procedure itself.

In case of a fatality, the cause of death is considered as the AE, and the death is considered as its outcome.

Pre-treatment Adverse Event

A pre-treatment adverse event is any untoward medical occurrence arising or observed between signing of informed consent and the first administration of the IMP.

Treatment Emergent Adverse Event

A treatment emergent adverse event is any AE occurring after the administration of the IMP and within the time of residual drug effect, or a pre-treatment adverse event or pre-existing medical condition that worsens in intensity after administration of the IMP and within the time of residual drug effect.

The time of residual drug effect is the estimated period of time after the administration of IMP, where the effect of the product is still considered to be present based on PK, PD or other substance characteristics. The residual drug effect is generally accepted to be 5 times the terminal half-life. Based on the data from healthy subjects, the terminal half-life of IdeS is expected to be approximately 5 days (mean of 118 hours in healthy subjects), i.e., in this study the residual drug effect is likely to be well within the 30 day visit.

Post-treatment Emergent Adverse Events

A post-treatment emergent adverse event is any event occurring after the time of residual drug effect of the IMP, i.e., from the visit on day 30.

8.4.2 Definition of Serious Adverse Events

A serious adverse event (SAE) is an AE or suspected adverse reaction (SAR) that is considered "serious" if, in the view of either the investigator or sponsor, it results in any of the following outcomes:

- Results in death
- Is immediately life-threatening
- Requires in-patient hospitalisation or prolongation of existing hospitalisation.
- Results in persistent or significant disability or incapacity
- Is a congenital abnormality or birth defect
- Is an important medical event that may jeopardise the patient or may require medical intervention to prevent one of the outcomes listed above

Important medical events that may not result in death, be life-threatening, or require hospitalization may be considered as SAEs when, based upon appropriate medical judgment, they may jeopardize the subject or may require medical or surgical intervention to prevent one of the outcomes listed in this definition. Examples of such events include allergic bronchospasm requiring intensive treatment in an emergency room or at home, blood dyscrasias or convulsions that do not result in inpatient hospitalization, or the development of drug dependency or drug abuse.

Life-threatening event: An adverse event or suspected adverse reaction is considered "life-threatening" if, in the view of either the investigator or sponsor, its occurrence places the patient or subject at immediate risk of death. It does not include an adverse event or suspected adverse reaction that, had it occurred in a more severe form, might have caused death.

Disability is defined as a substantial disruption in a person's ability to conduct normal life functions.

Hospitalization for inpatient hospitalization or prolongation of existing hospitalization.

- In this study for elective treatment of a pre-existing condition that did not worsen during the clinical investigation is not considered an AE. Hospitalisation for study drug dosing and observation as required by protocol is not considered an SAE. Admittance to an emergency room for observation without being admitted to the hospital may be considered to be an AE but is not considered as an SAE. However, complications that occur during hospitalization are AEs, and if a complication prolongs hospitalization, the event is considered serious.

Important medical events that may not result in death, be life-threatening, or require hospitalization may be considered serious when, based upon appropriate medical judgment, they may jeopardize the patient or subject and may require medical or surgical intervention to prevent one of the outcomes listed in this definition. Examples of such medical events

include allergic bronchospasm requiring intensive treatment in an emergency room or at home, blood dyscrasias or convulsions that do not result in inpatient hospitalization, or the development of drug dependency or drug abuse.

SAEs should be followed until the event resolves, stabilizes, or returns to baseline. If the patient is discontinued from the study prior to resolution/stabilization of the SAE, then the patient will be followed as part of the SAE/pharmacovigilance system.

8.4.3 Recording of Adverse Events

In clinical studies, an AE/SAE can occur at any time after signing of the informed consent until the end of the study, including run-in or washout periods, even if no study treatment has been administered, e.g., an AE can be related to a procedure in the protocol.

AEs will therefore be collected on the AE CRF from the time of signing of the informed consent and throughout the study period including the follow-up period. However, AEs that occur in the time period between informed consent and administration of the trial drug should be recorded as part of the patient's medical history, but will not be considered a treatment emergent adverse event (TEAE) unless directly related to study procedures (e.g., hematoma secondary to laboratory testing) or it meets the definition of an SAE.

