7.2 Study Procedures

For each patient the duration of the treatment period including screening and follow up visits will be approximately 3 months. Timing (45 min, 2 h, 6 h and 24 h respectively as indicated in the flow chart in Table 2) of sampling on day 0 relates to start of infusion.

Visit 1 (Screening Day -28 – 4)

All patients considered for the study must give their written consent before screening or any other study procedure is performed. Screening of a patient can take place up to 28 days before the first dosing on study day 0. To be eligible for the study patients have to meet all inclusion criteria and no exclusion criteria. A patient failing screening may not be rescreened. However, if a patient has been screened and found eligible he or she can be rescreened if dosing could not be performed within 28 days due to logistical reasons.

At the screening visit each subject will be informed about the study and after signing the informed consent form assessments for eligibility will commence. The eligibility evaluation includes adherence to inclusion and exclusion criteria, collection of concomitant medication, demographic data and medical history. A full physical examination, height and weight measurements, vital signs including resting blood pressure, pulse, respiratory frequency, 12-lead resting ECG and body temperature will be measured. AEs that occur in the time period between informed consent and administration of the trial drug should be recorded as part of the patient's medical history, but will not be considered a treatment emergent adverse event (TEAE) unless directly related to study procedures (e.g., hematoma secondary to laboratory testing) or it meets the definition of an SAE.

Additionally, blood sampling for serology (HIV, hepatitis), pregnancy test, clinical chemistry (including [REDACTED] and immunoglobulins), haematology (including [REDACTED])

and urine sampling for urinalysis as well as blood samples for analysis of ADAMTS13 activity, ADAMTS13 antibodies, and anti-IdeS IgE will be collected.

Visit 2 (Residential stay Day 0 to Day 1)

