8.4.4 Variables

The following variables will be recorded in the CRF for each AE; description of the AE, the date and time (if applicable) when the AE started and stopped, severity based on Common Toxicity Criteria grade (according to CTCAE v.4.0, see appendix 1) whether the AE is serious or not, causality rating, action taken with regard to investigational product, e.g., the AE caused patient to discontinue the study, and outcome.

For each reported AE the investigator will assess a causal assessment of the relationship of the event to study procedures and/or IdeS using the following criteria.

- **Unrelated:** applicable to an AE that occurs when the subject was not exposed to study treatment or another cause is obvious.
- **Unlikely to be related:** applicable to an AE that meets the following criteria
 - Does not follow a reasonable temporal sequence from study drug dosing
 - May readily have been produced by the patient's clinical state, environmental, or toxic factors, or other therapy administered to the patient
- **Possibly related:** applicable to AEs where connection with dosing of study drug appears unlikely but cannot be ruled out. Applicable to AEs where:
 - It follows a reasonable temporal sequence dosing with study drug
 - It follows a known pattern of response to study drug dosing (based on animal studies)

- **Probably related:** applicable to AEs that are considered, with a high degree of certainty, to be related to the study drug. Applicable to AEs where
 - It follows a reasonable temporal sequence study drug dosing
 - It cannot be reasonably explained by the know characteristics of the patient’s clinical state, environmental or toxic factors, or other modes of therapy
 - It follows a known patter of response to study drug dosing (based on animal data).
- For SAEs causal relationship will also be assessed for any study procedure.

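### Does the TEAE sentence in Protocol 7.2 and 8.4.3, with no adverse event listing named in SAP 4.2, leave the safety reporting undetermined?

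*Protocol*

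**What the plan says.** Protocol 8.4.1 defines three categories. A pre-treatment event is "any untoward medical occurrence arising or observed between signing of informed consent and the first administration of the IMP". A treatment-emergent event either starts after dosing and within the time of residual drug effect, or is a "pre-treatment adverse event or pre-existing medical condition that worsens in intensity after administration of the IMP" within that same period. A post-treatment event is "any event occurring after the time of residual drug effect of the IMP, i.e., from the visit on day 30".

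Protocol 8.4.3 adds a rule for the pre-dose window: "AEs that occur in the time period between informed consent and administration of the trial drug should be recorded as part of the" medical history, "but will not be considered a treatment emergent adverse event (TEAE) unless directly related to study procedures". Protocol 7.2 repeats the sentence under the screening visit and ends it with the example and the second exception, "e.g., hematoma secondary to laboratory testing) or it meets the definition of an SAE". Neither place mentions worsening, and no rule says which section prevails.

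Protocol 14.2.3 would list adverse events separately by the three categories. The SAP was written after the sponsor had stopped the trial at two patients. Its Section 1 withdraws the protocol's analyses, and Section 4.1 drops the summaries and tabulations. Section 4.2 names ten listings: disposition, demography, medication, medical history, exposure, PK, PD, safety laboratory, ECG and vital signs. SAP 3, 4.1 and 5 each say in general terms that all data will be shown.

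**The concern.** The type, frequency and intensity of adverse events form the first part of the primary endpoint, and the trial was stopped on a risk-benefit judgement in its first two patients. One would expect such a trial to state clearly which events count as treatment-emergent and where they are listed.

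The protocol's own example, a haematoma from blood sampling at screening, is pre-treatment under 8.4.1 but, on an ordinary reading of 7.2 and 8.4.3, treatment-emergent. A pre-dose SAE meets the same conflict. The SAP, which could have settled it, has no emergence definition and no listing titled adverse events. In a trial with treatment-emergent rates as outputs, this could move events into or out of the main safety table and attribute to the drug something that happened before it was given.

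**Working it through.** No calculation in the plan bears on this, so the check sets the rules side by side and then traces where the category is used.

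**Step 1. Classify each kind of pre-dose event under both texts.**

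| Pre-dose event | 8.4.1 | 7.2 and 8.4.3, ordinary reading | Agree? |
|---|---|---|---|
| Neither serious nor procedure-related, no worsening | Pre-treatment | Not a TEAE | Yes |
| Neither serious nor procedure-related, worsens after dosing within the residual effect | TEAE | Not a TEAE | No |
| Procedure-related, no worsening | Pre-treatment | TEAE | No |
| SAE, no worsening | Pre-treatment | TEAE | No |
| Procedure-related or SAE, worsens after dosing within the residual effect | TEAE | TEAE | Yes |

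Three rows disagree, and not all in the same direction: two add TEAEs and one removes them. The disagreement is softer than the table suggests. In strict logic, 'not X unless B' makes B necessary for X, not sufficient. On that reading the third and fourth rows are merely not excluded, and 8.4.1 still asks for worsening. The second row arises only because the sentence is silent on worsening, which 8.4.1 addresses directly.

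**Step 2. Check the other end of the window.** Protocol 8.4.1 takes five half-lives of 118 h: 5 × 118 = 590 h, and 590 / 24 = 24.6 days. That is 30 − 24.6 = 5.4 days before the day 30 visit, consistent with "the residual drug effect is likely to be well within the 30 day visit". The section itself then sets the post-treatment boundary at that visit, so no second conflict arises.

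**Step 3. Trace the uses of the category.**

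- Protocol 14.2.3, AE presentation by emergence: superseded by SAP 1, 4.1 and 5. SAP 4.2 sorts listings by parameter, subject and time point.
- Dose-limiting toxicity (Protocol 5.4): depends on grade, novelty and a possible relationship to the drug, not on emergence.
- Monitoring committee trigger (Protocol 5.5): depends on grade and relatedness. Under Protocol 8.4.4, an event in a patient not yet exposed to study treatment falls under unrelated.
- SAE reporting (Protocol 8.4.8): runs from consent, whatever the category.

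Remaining planned uses: none.

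**Step 4. Check whether the event data would still be shown.** Of the ten named listings, none is for adverse events. The SAP's three general statements nevertheless cover them. Protocol 8.4.4 requires "the date and time (if applicable) when the AE started and stopped, severity based on Common Toxicity Criteria grade", plus seriousness, causality, action taken and outcome. Dosing is in the exposure listing, and pre-dose events recorded as history are in the medical history listing. With two patients, a reader can compare onset with dosing directly.

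**The case for a change.** The best argument for acting is that SAP 4.1 drops summaries and tabulations but keeps listings, and the split in Protocol 14.2.3 is itself a set of listings. The SAP never says in terms that the split is abandoned. Section 4.2 reads as a definite list and omits part of the primary endpoint. Section 5 says the clinical report will show only a relevant subset of the data. A general promise to list everything is weaker than a named listing, and adding one title would cost almost nothing.

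Part of this stands. The sentence in 7.2 and 8.4.3 is poorly drafted. It was probably meant to decide what is recorded as an adverse event rather than as history, which fits the heading of 8.4.3, but the exception is attached to TEAE status instead. Section 8.4.3 also first collects all events from consent on the AE form and then directs pre-dose events to history. A named listing would have been tidier.

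The rest does not carry. SAP 1 and 5 say the reporting departs from the protocol's presentations, and sorting by parameter, subject and time point leaves no emergence split to fill. The only omission Section 5 names for the report is efficacy. Restoring an emergence column, with rules and flags, would rebuild a classification that the SAP has dropped. It would also lean on data that may not exist: Protocol 8.4.4 lists no date of worsening, asks for onset time only where applicable, and clearly establishes a separate procedure-relationship assessment only for SAEs.

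**Conclusion.** The inconsistency is real but has no consequence, and no change to the plan is needed. The TEAE wording is a drafting slip: the texts differ for three narrow kinds of pre-dose event, and no planned output or safety rule depends on the answer. An analyst who needed a category would naturally take it from 8.4.1, the section that defines all three. The missing listing title is a gap that analysts fill sensibly, given the SAP's three commitments to show all data and the AE fields the protocol already collects.

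This rests on three assumptions: the general commitments are honoured for adverse events, reporting stays limited to listings and plots for the two treated patients, and no treatment-emergent counts are produced. If enrolment resumed or the AE summaries of Protocol 14.2.3 were reinstated, the sentence would matter and would have to be reconciled with 8.4.1. A small residual limit is that an event on day 0 with no recorded time could not be placed before or after dosing; rewording the definitions would not cure that.

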8.4.4 Variables

The following variables will be recorded in the CRF for each AE; description of the AE, the date and time (if applicable) when the AE started and stopped, severity based on Common Toxicity Criteria grade (according to CTCAE v.4.0, see appendix 1) whether the AE is serious or not, causality rating, action taken with regard to investigational product, e.g., the AE caused patient to discontinue the study, and outcome.

For each reported AE the investigator will assess a causal assessment of the relationship of the event to study procedures and/or IdeS using the following criteria.

- **Unrelated:** applicable to an AE that occurs when the subject was not exposed to study treatment or another cause is obvious.
- **Unlikely to be related:** applicable to an AE that meets the following criteria
 - Does not follow a reasonable temporal sequence from study drug dosing
 - May readily have been produced by the patient's clinical state, environmental, or toxic factors, or other therapy administered to the patient
- **Possibly related:** applicable to AEs where connection with dosing of study drug appears unlikely but cannot be ruled out. Applicable to AEs where:
 - It follows a reasonable temporal sequence dosing with study drug
 - It follows a known pattern of response to study drug dosing (based on animal studies)

- **Probably related:** applicable to AEs that are considered, with a high degree of certainty, to be related to the study drug. Applicable to AEs where
 - It follows a reasonable temporal sequence study drug dosing
 - It cannot be reasonably explained by the know characteristics of the patient’s clinical state, environmental or toxic factors, or other modes of therapy
 - It follows a known patter of response to study drug dosing (based on animal data).
- For SAEs causal relationship will also be assessed for any study procedure.

